## 1.7 Primary Endpoints

### 1.7.1 Primary Effectiveness Endpoint

The Primary effectiveness endpoint is TLPP evaluated at 6 months (Refer to Section 4.1.1 for applicable definitions). In order to demonstrate clinically acceptable effectiveness, this randomized study will assess superiority of the rate of TLPP at 6 months of the COVERA™ Vascular Covered Stent as compared to standard PTA alone.

### 1.7.2 Primary Effectiveness Endpoint Hypothesis Test

The primary effectiveness endpoint is TLPP through 6-months. Objective: To assess if the 6 month TLPP for the COVERA™ Vascular Covered Stent is superior to that of PTA alone, by direct comparison.

The primary effectiveness endpoint will be evaluated by the following hypothesis:

**H0:** The (survival) rate  $S_1(t)$  of subjects in the study device treatment group with TLPP through  $t \leq 6$  month post index procedure is less than or equal to that  $S_2(t)$  of PTA treatment group.

**H1:** The (survival) rate  $S_1(t)$  of subjects in the study device treatment group with TLPP through  $t \leq 6$  month post index procedure is greater than that  $S_2(t)$  of PTA treatment group.

That is:

**H0:**  $S_1(t) \leq S_2(t)$ , for  $t \leq 6$  months

**H1:**  $S_1(t) > S_2(t)$ , for  $t \leq 6$  months

Rejection of the null hypothesis will signify that the 6 month TLPP of the COVERA™ Vascular Covered Stent is superior to the 6 month TLPP of PTA alone.

A Kaplan-Meier analysis will be used to estimate the survival rate of TLPP in the COVERA™ Vascular Covered Stent and PTA alone groups. A log-rank test will be used to test the primary effectiveness hypothesis to determine if COVERA™ Vascular Covered Stent is superior to PTA. The test is successful if the one-sided p-value is less than 0.025 and the result is in favor of the COVERA™ Vascular Covered Stent. In addition to the p-value of the test, the confidence intervals of the rate in each group will be provided.

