Enrollment:	A total of 280 subjects will be randomized to the study. The primary endpoint analysis will occur when 280 randomized subjects have completed or discontinued before their 6 month follow up. The key secondary endpoint analysis will occur when 280 randomized subjects have completed or discontinued before their 12 month follow up. All subjects will be followed for 24 months post index-procedure.
Investigational Sites:	Up to 35 investigational sites in the United States (US), Europe, and Australia/New Zealand will participate. Treated subjects will be distributed globally with 50-75% of the treated subjects in the U.S.
Study Population:	Male or non-pregnant female $\geq 21$ years of age with an expected lifespan sufficient to allow for completion of all study procedures. Eligible subjects will have a hemodynamically significant stenosis.
Inclusion Criteria	
Clinical Inclusion Criteria
 
 
1. Subject must voluntarily sign and date the Informed Consent Form (ICF) prior to collection of study data or performance of study procedures.
 
2. Subject must be either a male or non-pregnant female <math>\geq 21</math> years of age with an expected lifespan sufficient to allow for completion of all study procedures.
 
3. Subject must be willing to comply with the protocol requirements, including clinical and telephone follow-up.
 
4. Subject must have an upper extremity AV fistula that has undergone at least one successful dialysis session with two-needle cannulation, prior to the index procedure.
 
 
Angiographic Inclusion Criteria
 
 
5. Subject must have angiographic evidence of a stenosis <math>\geq 50\%</math> (by visual estimation) located in the venous outflow of the AV access circuit and present with clinical or hemodynamic evidence of AV fistula dysfunction.
 
6. The target lesion must be <math>\leq 9</math>cm in length. Note: multiple stenoses may exist within the target lesion.
 
7. The reference vessel diameter of the adjacent non-stenotic vein must be between 5.0 and 9.0mm.
 

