#### 1.4 Assessment of the Comparability of Treatment Groups and Poolability of Investigational Sites

To demonstrate the comparability of the Control to Test subjects, the treatment groups will be compared with respect to demographics and baseline characteristics and other covariates using t-tests or Wilcoxon nonparametric tests for means and  $\chi^2$ -tests for proportions.

Demographics, baseline characteristics and other covariates will also be compared between the treatment groups by sites using descriptive statistics. Both primary endpoints will also be summarized by treatment group and by site. This can help identify any confounding covariates that can potentially explain the variability of the treatment effect across sites. Sites with fewer than 10 treated subjects may be combined for this purpose. The pooling will be restricted within country.

For the primary effectiveness endpoint, an analysis will be performed to examine the potential for interaction of site and treatment group. A Cox regression model will be fit that includes fixed effect for treatment group, site and the interaction of treatment group and site. If the p-value for the interaction term is  $<0.15$ , it will be considered evidence of a possible significant interaction effect, and additional analyses will be performed to explore the differences between sites to assess their potential causes and whether or not they are clinically meaningful.

For the primary safety endpoint, an analysis will be performed as well to examine the potential for interaction of site and treatment group. A logistic regression model will be fit that includes fixed effect for treatment group, site and the interaction of treatment group and site. If the p-value for the interaction term is  $<0.15$ , it will be considered evidence of a possible significant interaction effect, and additional analyses will be performed to explore the differences between sites to assess their potential causes and whether or not they are clinically meaningful.

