Both primary endpoints will also be presented by geography (US versus OUS). Similar analyses will be performed to examine the potential for interaction of geography and treatment group for both endpoints. A Cox regression model for the primary effectiveness endpoint and a logistic regression model for the primary safety endpoint will be fit that includes fixed effect for treatment group, geography and the interaction of treatment group and geography. If the p-value for the interaction term is  $<0.15$ , it will be considered evidence of a possible significant interaction effect, and additional analyses will be performed to explore the differences between geographies to assess their potential causes and whether or not they are clinically meaningful.

---

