### 1.8.1 Key Secondary Endpoint with Hypothesis Test: TLPP at 12 Months

The key secondary effectiveness endpoint is TLPP through 12-months. Objective: To assess if the 12 month TLPP for the COVERA™ Vascular Covered Stent is superior to that of PTA alone, by direct comparison.

The primary effectiveness endpoint will be evaluated by the following hypothesis:

**H0:** The (survival) rate  $S_1(t)$  of subjects in the study device treatment group with TLPP through  $t \leq 12$  month post index procedure is less than or equal to that  $S_2(t)$  of PTA treatment group.

**H1:** The (survival) rate  $S_1(t)$  of subjects in the study device treatment group with TLPP through  $t \leq 12$  month post index procedure is greater than that  $S_2(t)$  of PTA treatment group.

That is:

**H0:**  $S_1(t) \leq S_2(t)$ , for  $t \leq 12$  months

**H1:**  $S_1(t) > S_2(t)$ , for  $t \leq 12$  months

Rejection of the null hypothesis will signify that the 12 month TLPP of the COVERA™ Vascular Covered Stent is superior to the 12 month TLPP of PTA alone.

A Kaplan-Meier analysis will be used to estimate the survival rate of TLPP in the COVERA™ Vascular Covered Stent and PTA alone groups. A log-rank test will be used to test the key secondary effectiveness hypothesis to determine if the COVERA™ Vascular Covered Stent is superior to PTA. The test is successful if the one-sided p-value is less than 0.025 and the result is in favor of the COVERA™ Vascular Covered Stent. In addition to the p-value of the test, the confidence intervals of the rate in each group will be provided. Note that, unless both the primary endpoints are successful, hypothesis for the key secondary effectiveness will be tested for exploratory purpose only.

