#### 1.8.2 Key Secondary Endpoint with Hypothesis Test: ACPP at 6 Months

The key secondary endpoint is ACPP evaluated at 6 months (Refer to Section 4.2.1 for applicable definitions). Objective: To assess if the 6 months ACPP rates for the COVERA™ Vascular Covered Stent is superior to the primary patency rate for standard PTA, by direct comparison:

**H0:** The (survival) rate  $S_1(t)$  of subjects in the study device treatment group with ACPP through  $t \leq 6$  month post index procedure is less than or equal to that  $S_2(t)$  of PTA treatment group.

**H1:** The (survival) rate  $S_1(t)$  of subjects in the study device treatment group with ACPP through  $t \leq 6$  month post index procedure is greater than that  $S_2(t)$  of PTA treatment group.

That is:

**H0:**  $S_1(t) \leq S_2(t)$ , for  $t \leq 6$  months

**H1:**  $S_1(t) > S_2(t)$ , for  $t \leq 6$  months

Rejection of the null hypothesis will signify that the 6 month ACPP of the COVERA™ Vascular Covered Stent is superior to the 6 month ACPP of standard PTA alone.

A Kaplan-Meier analysis will be used to estimate the survival rate of ACPP in the COVERA™ Vascular Covered Stent and PTA alone groups. A log-rank test will be used to test this hypothesis to determine if the COVERA™ Vascular Covered Stent is superior to PTA alone. The test is successful if the two-sided p-value is less than 0.05 and the result is in favor of the COVERA™ Vascular Covered Stent. In addition to the p-value of the test, the confidence intervals of the rate in each group will be provided. Note that, unless both the primary endpoints, and the TLPP at 12-month endpoint are all successful, the hypothesis for the ACPP at 6-month will be tested for exploratory purpose only.

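### The three confirmatory patency tests are valid but unadjusted log-rank tests; prespecified adjustment for geography and lesion measures would be a cheap, modest gain in power

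*Combined protocol and SAP*

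**What the plan says.** Three superiority tests carry confirmatory weight, and each is a log-rank test with no strata or covariates:

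- TLPP through 6 months (SAP 1.7.2): "A log-rank test will be used to test the primary effectiveness hypothesis". The criterion is "The test is successful if the one-sided p-value is less than 0.025", with the result favouring the device.
- TLPP through 12 months (1.8.1): "A log-rank test will be used to test the key secondary effectiveness hypothesis", with the same one-sided threshold.
- ACPP through 6 months (1.8.2): "A log-rank test will be used to test this hypothesis". The criterion is two-sided 0.05 in the device's favour, which equals one-sided 0.025.

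Section 1.3 gives a 1:1 ratio and no stratification factor.

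The Protocol Summary sets three angiographic criteria on measured quantities: percent stenosis, target lesion length and vessel diameter, the last as "The reference vessel diameter of the adjacent non-stenotic vein must be between 5.0 and 9.0mm". Exclusion criterion 16 places the primary angioplasty of the target lesion before randomization, so these assessments come first. Geography follows from the site.

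Baseline covariates appear only in section 1.4. They are compared between arms by t, Wilcoxon and chi-square tests "To demonstrate the comparability of the Control to Test subjects", and described by site with the comment "This can help identify any confounding covariates that can potentially explain the variability of the treatment effect across sites". Site and geography enter Cox models only as checks for interaction with treatment, at a 0.15 threshold. No adjusted or stratified version of the three tests is planned, even as a sensitivity analysis.

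**The concern.** If lesion length, vessel diameter, percent stenosis or geography predict loss of patency, a test that ignores them treats explainable variation as noise. A covariate-adjusted log-rank test keeps the same null hypothesis and threshold, and in large samples it is not less powerful. It also removes the part of a chance imbalance that the covariates explain. At present neither the stated randomization nor the confirmatory analysis deals with such an imbalance.

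The baseline tests in section 1.4 do not fill the gap. A non-significant p-value does not show that the arms are alike, and the plan does not say what would follow from a significant one.

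What is at stake is power if the true effects are smaller than planned. The 12-month test matters twice, because ACPP is confirmatory only if TLPP at 12 months succeeds. ACPP itself has no planning rates or stated power.

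**Working it through.** **1. The plan's own power (SAP 1.6).** Under proportional hazards, HR = ln(S1)/ln(S2), and events = evaluable subjects × mean failure rate.

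- 6 months: HR = ln 0.73/ln 0.50 = 0.454; events = 252 × (1 − 0.615) = 97.0.
- 12 months: HR = ln 0.55/ln 0.33 = 0.539; events = 238 × (1 − 0.44) = 133.3.

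Freedman: power = Φ(√d·(1 − HR)/(1 + HR) − 1.96). Schoenfeld: power = Φ(√d·|ln HR|/2 − 1.96).

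| | Stated | Freedman | Schoenfeld | Two proportions | Two proportions, continuity-corrected |
|---|---|---|---|---|---|
| TLPP 6 months | 95% | 95.9% | 97.3% | 96.7% | 95.6% |
| TLPP 12 months | 90% | 93.3% | 94.6% | 93.3% | 91.3% |

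The stated figures are reproduced or slightly conservative, so the plan is adequately powered at its own rates without adjustment.

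**2. Chance imbalance at 140 per arm.** The standard error of a standardized difference is √(2/140) = 0.1195.

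- A difference not significant at the 5% level (a level assumed here; section 1.4 states none) can be as large as 1.96 × 0.1195 = 0.23 SD.
- P(|difference| > 0.2 SD) = 9.4% for one covariate, and 1 − (1 − 0.094)³ = 26% for at least one of three if they are independent.

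**3. Effect of adjustment on power.** Simulation inputs from the documents: 280 subjects 1:1, the TLPP rates above, and dropout of 10% by 6 months or 15% by 12 months. Assumed: exponential event and dropout times, and hazard ratios for three continuous lesion covariates (per SD) and for geography of

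- moderate: 1.35, 1.2, 1.2 and 1.3;
- strong: 1.6, 1.3, 1.3 and 1.6.

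Marginal patency was calibrated to the rates shown. The adjusted test regresses the log-rank influence terms on the covariates within each arm. Power, unadjusted to adjusted, before any small-sample correction (4,000 trials per cell):

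| Device v PTA | Moderate | Strong |
|---|---|---|
| 73% v 50%, 6 months (planned) | 98.1 → 98.5% | 97.5 → 98.7% |
| 55% v 33%, 12 months (planned) | 96.6 → 97.7% | 97.1 → 98.8% |
| 66% v 50%, 6 months | 75.8 → 78.9% | 77.4 → 83.8% |
| 48% v 33%, 12 months | 73.9 → 76.9% | 75.1 → 83.0% |

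One-sided error was 2.4–2.9% adjusted against 2.4–2.7% unadjusted, so part of these gains comes from a slightly liberal test. With a degrees-of-freedom correction to the variance:

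- error was 2.4–2.7% for both tests;
- the gain was about 0.3–1.7 points at the planned rates;
- at the smaller effects the gain was about 1.4–3.3 points (moderate) and 4.5–7.1 points (strong);
- covariates with no prognostic value cost about 0.1–0.7 points.

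**4. ACPP, illustration only.** The documents give no rates. With an assumed 60% v 45%, and a log-rank test stratified on two binary factors (a different method from step 3), power moved as follows:

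| HR per factor | Unadjusted → stratified |
|---|---|
| 1.0 | 70.6 → 70.2% |
| 1.5 | 70.7 → 71.8% |
| 2.0 | 71.5 → 76.3% |
| 3.0 | 71.6 → 84.6% |

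**The case against.** The strongest reply is that nothing is broken. A reader might infer from the 9% and 26% imbalance figures that the planned test is biased or inflates the error rate. It does neither: under randomization, chance imbalance is already part of the 2.5% error, and the simulated error of the plain test was close to nominal. This stands in full.

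A reader might also infer that the gain is free and assured. The documents do not support that. They do not say that any of these factors predicts patency, and an uncorrected adjusted test ran slightly above nominal error. At the planned rates the gain hardly moves the chance of trial success, because safety is the limiting endpoint. Using the plan's 91% for safety and multiplying as the plan does, joint power goes from 0.981 × 0.91 = 89.3% to 0.985 × 0.91 = 89.6% (moderate), or from 0.975 × 0.91 = 88.7% to 0.987 × 0.91 = 89.8% (strong). These use the uncorrected figures.

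Other points that stand:

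- The eligibility criteria require only that thresholds are met. That the measured values are recorded for every subject is an inference, and the Protocol Summary also lists an angiographic core laboratory, so the source of the reading has to be named.
- It is tempting to say that ACPP gains most, or that treated non-target lesions should be added as a covariate for it. The ACPP definition in Section 4 was not in the text reviewed, and no rates are given, so neither can be established.
- The remark in section 1.4 on confounding covariates concerns differences between sites. It does not announce a post hoc adjustment of the main test.
- Since Section 4 was not available, stratification described elsewhere cannot be excluded.

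What the reply does not answer is that a test with the same null hypothesis and threshold is available for little more than SAP wording. With the correction it holds its error rate. Its likely loss is under a point, and its possible gain is several points where power is most needed.

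**Conclusion.** The point holds as a recommendation on efficiency. The three log-rank tests are valid, and the stated TLPP power does not depend on adjustment. The case for change rests on smaller true effects than planned and on covariates of at least moderate prognostic strength; both are assumptions outside the documents. The balance still favours adjustment, since the downside is small and bounded while the upside grows as power falls. For ACPP the direction is plausible but no size can be given.

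Separately, baseline significance tests cannot demonstrate comparability at this sample size, whichever test is chosen for the endpoints.

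**What to change.** In sections 1.7.2, 1.8.1 and 1.8.2, before any 6-month outcome data are analysed:

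- Name a covariate-adjusted log-rank test as the confirmatory test, with the same null hypothesis and the same one-sided 0.025 threshold (for ACPP, the equivalent two-sided 0.05).
- Adjust for geography (US or OUS) and for target lesion length, reference vessel diameter and percent stenosis, as recorded at the site before randomization. Confirm that the case report form captures the measured values, and state a rule for missing ones.
- Make a degrees-of-freedom correction to the variance mandatory and write out its formula. One option is the factor (n − 2)/(n − 2 − q), with q the number of fitted slopes. With four covariates fitted in each of two arms, q = 8, and at n = 280 the factor is 278/270 = 1.03.
- Keep the unadjusted log-rank test as the sensitivity analysis.

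In section 1.4, replace the baseline p-values with standardized differences, and state that covariates will not be chosen, added or dropped because of them.

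The cost is SAP wording and some programming, with no new visits or subjects, provided the lesion values are recorded. The price is a loss of up to about 0.7 points of power if the covariates are not prognostic, and an adjusted p-value reported beside unadjusted Kaplan-Meier rates, which the report should explain.

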### 1.7.3 Primary Safety Endpoint

The primary safety endpoint is proportion of subjects who are free from localized or systemic adverse events through 30 days that reasonably suggests the involvement of the AV access circuit (Refer to Section 4.1.2 for applicable definitions).

### 1.7.4 Primary Safety Endpoint Hypothesis Test

The primary safety endpoint is safety through 30 days. Objective: To assess if the 30-day primary safety rate for the study device is non-inferior to that of PTA alone, by direct comparison:

**H0:** The primary safety rate  $p_1$  in the Test group through 30 days post index procedure is inferior to that  $p_2$  of the PTA treatment group.

**H1:** The primary safety rate  $p_1$  in the Test group through 30 days post index procedure is non-inferior to that  $p_2$  of the PTA treatment group.

That is:

**H0:**  $p_1 \leq p_2 - \delta$

**H1:**  $p_1 > p_2 - \delta$

Where  $\delta = 10\%$  is the non-inferiority margin, which is the range of difference that is considered not clinically important.

Non-inferiority Farrington and Manning Exact Test will be used to test the primary safety hypothesis. The test is successful if the one-sided p-value is less than 0.025. In addition to the p-value of the test, the confidence intervals of the rate in each group and the difference between the two groups will be provided.

## 1.8 Evaluation of Secondary Endpoints

All secondary endpoints will be tested as exploratory only unless both primary hypotheses are successful. The testing of the secondary objectives will be performed in a hierarchical fashion in the order in which they are listed below. This means that as soon as a null hypothesis is *not rejected*, all further hypotheses will be tested for exploratory purpose only. This hierarchical testing scheme ensures that the study-wide Type 1 error rate remains at 0.05 when all of the secondary endpoints are tested at  $\alpha=0.05$ .

### 1.8.1 Key Secondary Endpoint with Hypothesis Test: TLPP at 12 Months

The key secondary effectiveness endpoint is TLPP through 12-months. Objective: To assess if the 12 month TLPP for the COVERA™ Vascular Covered Stent is superior to that of PTA alone, by direct comparison.

The primary effectiveness endpoint will be evaluated by the following hypothesis:

**H0:** The (survival) rate  $S_1(t)$  of subjects in the study device treatment group with TLPP through  $t \leq 12$  month post index procedure is less than or equal to that  $S_2(t)$  of PTA treatment group.

**H1:** The (survival) rate  $S_1(t)$  of subjects in the study device treatment group with TLPP through  $t \leq 12$  month post index procedure is greater than that  $S_2(t)$  of PTA treatment group.

That is:

**H0:**  $S_1(t) \leq S_2(t)$ , for  $t \leq 12$  months

**H1:**  $S_1(t) > S_2(t)$ , for  $t \leq 12$  months

Rejection of the null hypothesis will signify that the 12 month TLPP of the COVERA™ Vascular Covered Stent is superior to the 12 month TLPP of PTA alone.

A Kaplan-Meier analysis will be used to estimate the survival rate of TLPP in the COVERA™ Vascular Covered Stent and PTA alone groups. A log-rank test will be used to test the key secondary effectiveness hypothesis to determine if the COVERA™ Vascular Covered Stent is superior to PTA. The test is successful if the one-sided p-value is less than 0.025 and the result is in favor of the COVERA™ Vascular Covered Stent. In addition to the p-value of the test, the confidence intervals of the rate in each group will be provided. Note that, unless both the primary endpoints are successful, hypothesis for the key secondary effectiveness will be tested for exploratory purpose only.

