
Secondary Endpoints:
	
Key Secondary Endpoint with Hypothesis Testing
 
 
• TLPP through 12 months.
 
• Access Circuit Primary Patency (ACPP) through 6 months.
 
 
Secondary Endpoints without Hypothesis Testing
 
 
• TLPP through 30 days, 90 days, 18 months, and 24 months.
 
• ACPP through 30 days, 90 days, 12 months, 18 months, and 24 months.
 
• Rate of device and procedure related AEs involving the AV access circuit through 90 days, 6 months, 12 months, 18 months, and 24 months.
 
• Total Number of AV Access Circuit Reinterventions through 30 days, 90 days, 6 months, 12 months, 18 months, and 24 months.
 
• Total Number of Target Lesion Reinterventions through 30 days, 90 days, 6 months, 12 months, 18 months, and 24 months.
 
• Index of Patency Function (IPF) evaluated at 30 days, 90 days, 6 months, 12 months, 18 months, and 24 months.
 
• Index of Patency Function – Target Lesion (IPF-T) evaluated at 30 days, 90 days, 6 months, 12 months, 18 months, and 24 months.
 
• Secondary Patency evaluated through 30 days, 90 days, 6 months, 12 months, 18
 

---

	months, and 24 months. 

• Acute Technical Success.

• Acute Procedure Success (Anatomic and Clinical Success).

Lead Principal Investigator:	[REDACTED]
Angiographic Core Lab	[REDACTED]

---

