## 1.5 Handling of Missing Data

Study endpoints may be missing due to withdrawal of consent, Investigator's decision, LTF and subject death. It is important to minimize missing data by all means and always record the reason for missing. Missing data will be handled as described subsequently.

The primary analysis of the primary effectiveness endpoint is a survival analysis. As a sensitivity analysis, the primary safety endpoint will also be analyzed using survival analysis techniques. In survival analyses, unobserved endpoints are a standard part of the analysis; they are known as "censored observations". As long as the censoring is unrelated to the treatment, this method of handling missing endpoints produces unbiased estimates of the freedom-from-event rates. In addition, as a sensitivity analysis, the primary effectiveness endpoint will be analyzed as a proportion-based binomial rate.

For both primary endpoints, the reason for the censoring of all subjects with missing endpoints will be reported. If there is any indication that the censoring is related to the treatment group, a worst-case analysis may be performed for each primary endpoint, in addition to the standard analysis. In a worst-case analysis, an event will be assumed to have occurred at the time the subject was censored for all such subjects in the Test group. In the Control group, all subjects with missing data will be assumed *not* to have had an event.

In addition, regardless of whether missing data are related to the study intervention, a tipping-point analysis will also be performed, in which assumptions about missing data are varied from worst-case to best-case to examine at what point the missing data would alter the results of the analysis.

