### 1) Key Secondary Endpoint – TLPP at 12 months:

- Assumptions:
  - TLPP rate through 12 months for the study device treated subjects is 55%;
  - TLPP rate through 12 months for the PTA only treated subjects is 33%;
  - Allocation ratio: 1:1;
  - Attrition (drop-out) rate (by 12 months) = 15%
  - The Type 1 error,  $\alpha = 0.025$  (one-sided); and
  - The Type 2 error,  $\beta = 0.10$  (Power =  $1 - \beta = 90\%$ ).
- Sample Size:
  - 280 randomized subjects [238 evaluable] will give 90% power with one-sided type I error = 0.025.

2) Primary Effectiveness Endpoint – TLPP at 6 months:

- Assumptions:
  - TLPP rate through 6 months for the study device treated subjects is 73%;
  - TLPP rate through 6 months for the PTA only treated subjects is 50%;
  - Allocation ratio: 1:1;
  - Attrition (drop-out) rate (by 6 months) = 10%
  - The Type 1 error,  $\alpha = 0.025$  (one-sided); and
  - The Type 2 error,  $\beta = 0.10$  (Power =  $1 - \beta = 95\%$ ).
- Sample Size:
  - 280 randomized subjects [252 evaluable] will give 95% power with one-sided type I error = 0.025.

3) Primary Safety Endpoint – Safety at 30 days:

- Assumptions:
  - The primary safety rate through 30 days in the study device treated subjects is 95%;
  - The primary safety rate through 30 days in the PTA only treated subjects is 95%;
  - Non-inferiority margin  $\delta = 10\%$ ;
  - Allocation ratio: 1:1;
  - Attrition rate (by day 30) = 5%; and
  - The Type 1 error,  $\alpha = 0.025$  (one-sided).
- Sample Size:
  - 280 randomized subjects [266 evaluable] will give 91% power with one-sided type I error = 0.025.

Hence, the sample size of 280 randomized subjects, allocated 1:1, for 140 subjects in the COVERA™ Vascular Covered Stent arm and 140 subjects in the PTA alone arm, will provide approximately 86% power for the both primary effectiveness and primary safety endpoint. The sample size of 280 randomized subjects, allocated 1:1 for 140 subjects in the COVERA™ Vascular Covered Stent arm and 140 in the PTA alone arm, will provide approximately 90% power for the key secondary endpoint.

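### Does section 1.8.1 need different wording, or a planned confidence interval for the 12-month difference, to support its claim of superior 12-month TLPP?

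*Combined protocol and SAP*

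**What the plan says.** The protocol summary lists the key secondary endpoint as "TLPP through 12 months". Section 1.8.1 opens in the same terms: "The key secondary effectiveness endpoint is TLPP through 12-months". Its objective is "To assess if the 12 month TLPP for the COVERA™ Vascular Covered Stent is superior to that of PTA alone, by direct comparison". The null and alternative hypotheses compare S1(t) with S2(t) for t up to 12 months. The method is "A log-rank test will be used to test the key secondary effectiveness hypothesis", with success at one-sided p below 0.025 in the device's favour. The section then interprets a positive result: "Rejection of the null hypothesis will signify that the 12 month TLPP of the COVERA™ Vascular Covered Stent is superior" to that of PTA alone.

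For estimation, the section plans Kaplan-Meier curves and adds: "In addition to the p-value of the test, the confidence intervals of the rate in each group will be provided". It lists no between-arm difference at 12 months, no interval for one, and no hazard ratio. Sections 1.7.2 (TLPP at 6 months) and 1.8.2 (access circuit primary patency, ACPP, at 6 months) follow the same pattern. Section 1.7.4 (safety) does list an interval for the difference. Section 1.5 says that "as a sensitivity analysis, the primary effectiveness endpoint will be analyzed as a proportion-based binomial rate", which concerns the 6-month endpoint and does not extend to month 12.

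**The concern.** A log-rank test compares event experience over the whole interval. Two curves can separate early, meet again by month 12, and still give a significant result. The section heading, the objective and the concluding sentence can all be read as statements about the month-12 rate, so a significant test could be reported as a month-12 benefit that is not there.

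The planned outputs add to the worry. The p-value does not say how large the 12-month benefit is, and the only planned intervals are for each arm separately. The safety section shows that the authors knew how to ask for an interval on the difference. At stake are the labelling of a key secondary claim that also opens the way to the ACPP test, and the reader's view of its size.

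**Working it through.** **Inputs, all from section 1.6.** TLPP at 6 months 73% (device) and 50% (PTA); at 12 months 55% and 33%; attrition 10% by 6 months and 15% by 12 months; 280 randomised 1:1, 238 evaluable at 12 months (119 per arm); one-sided alpha 0.025; stated power 90%.

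**The plan's own figure.** Two-proportion sample size for 90% power:

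n = [1.960 × √(2 × 0.44 × 0.56) + 1.282 × √(0.55 × 0.45 + 0.33 × 0.67)]² / 0.22² = 105 per arm.

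The continuity correction, (n/4) × [1 + √(1 + 4/(0.22n))]², raises this to 114. The available 119 per arm give about 91% with the correction and 93.3% without. A Schoenfeld log-rank calculation (HR = ln 0.55 / ln 0.33 = 0.539, about 133 events) gives 94.6%. The stated 90% is reproduced and is conservative for the log-rank test.

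**What the planned rates say about late convergence.**

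- Months 0-6: HR = ln 0.73 / ln 0.50 = 0.454.
- Months 6-12: HR = ln(0.55/0.73) / ln(0.33/0.50) = 0.681.

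The device is still favoured after month 6. For both arms to reach a common 12-month rate s, the later HR must be ln(s/0.73) / ln(s/0.50): 1.91, 2.70 and 3.96 for s = 33%, 40% and 44%.

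**Simulation.** 140 per arm, piecewise-exponential times through the stated rates, independent censoring at the stated attrition, follow-up cut at 12 months, 10,000 trials per scenario. Rows 2 to 5 use assumed 12-month rates, not plan values.

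| Scenario (12-month rates) | Log-rank rejects | Mean 12-month difference | Wins whose 95% CI includes 0 |
|---|---|---|---|
| Planned, 55% v 33% | 97.9% | 22.1 points | 3.2% |
| No benefit after month 6, 48% v 33% | 89.4% | 15.1 | 21.7% |
| Converged, 33% | 29.8% | 0.0 | 91.2% |
| Converged, 40% | 26.9% | 0.0 | 91.0% |
| Converged, 44% | 26.3% | 0.1 | 89.4% |
| Identical curves, 33% in both | 2.6% | – | – |

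The 48% is 0.73 × 0.33/0.50. If the 6-month test is won and safety is independent, the safety gate (stated power 91%) lowers the converged figures to 0.91 × 26.3% = 23.9% up to 0.91 × 29.8% = 27.1%. These are not false rejections of equal curves: the device curve is higher throughout the period before month 12.

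**Can the difference be read from the planned outputs?** Binomial approximation, 119 per arm:

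- Device half-width: 1.96 × √(0.55 × 0.45/119) = 8.9 points.
- PTA half-width: 1.96 × √(0.33 × 0.67/119) = 8.4 points.
- Difference: √(8.9² + 8.4²) ≈ 12.3 points, so 22 ± 12.3, or 9.7 to 34.3.

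The arms are independent, so the two arm intervals supply what is needed. The plan does not name its interval type. If log-log arm intervals are assumed and combined by the MOVER method, a 4,000-trial simulation at the planned rates gives limits that differ from direct Greenwood limits by 0.5 points on average, with 94.5% coverage. Under convergence to 33%, the derived interval includes 0 in 91% of wins, against 90% for the direct one.

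**Would other wording help?** One might restrict the conclusion to TLPP through 12 months. But section 1.6 uses that phrase for the month-12 rate itself ("TLPP rate through 12 months for the study device treated subjects is 55"%), and section 1.8.3 uses it in the same way for other time points. The documents draw no distinction between the two expressions, so the swap would leave the same two readings.

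**The case for a change.** The best case for a change is that it costs almost nothing. The plan sizes this endpoint on a 22-point difference at 12 months and never schedules an estimate of that difference with its uncertainty, although it does so for safety. Among winning trials at the planned rates, the observed difference runs from 13 to 32 points (5th to 95th percentile), and one p-value covers them all. An interval that a reader derives is not a pre-specified output. Under convergence, a direct interval would include 0 in about nine wins out of ten and so would warn the reader.

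The omission is real, and a descriptive difference with a 95% interval would be good reporting for all three patency tests. But the plan offers more than a p-value. It gives both Kaplan-Meier rates with intervals, from which the difference and nearly the same interval follow, and these carry the same warning under convergence. The convergence itself is assumed, and the plan's rates point the other way. The identical sentence and omission at the primary endpoint also suggest a reporting style rather than a fault peculiar to 12-month TLPP.

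**Conclusion.** The concern does not call for a change. Endpoint, hypotheses and test in section 1.8.1 agree with each other, and the concluding sentence is shorthand for the alternative hypothesis written just above it. No stated figure or decision rule is wrong. Alpha, power, sample size and the testing order are unaffected, and at the planned rates the claim is true in direction, by about 22 points (95% CI about 10 to 34).

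What remains is one unlisted descriptive output that analysts can produce from results already planned. If it is reported, it should be marked as descriptive, because it can include 0 beside a significant log-rank test (3.2% of wins at the planned rates).

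This rests on the section 1.6 rates and attrition, on censoring independent of outcome, and on there being no marked reversal of effect after month 6. The documents offer no evidence on that last point beyond their assumed rates. The definitions in sections 4.1.1 and 4.2.1, to which the SAP refers, are not in the text available and could not be checked.
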